3.3. Summary of LQT-1213 Preclinical Cardiovascular Safety

The potential for LQT-1213 to adversely affect cardiovascular system function was evaluated via in vivo GLP safety pharmacology assessments in male Sprague Dawley rats and telemetered male Beagle dogs. Single-doses of LQT-1213 at 0 (vehicle), 30, 100, and 300 mg/kg by oral gavage showed no adverse effects on the central nervous system, as measured by Functional Observational Battery assessments, or respiratory functions in Sprague Dawley rats. In telemetered Beagle dogs, single-doses of LQT-1213 administered at 0 (vehicle), 10, 30, or 100 mg/kg/day (5, 15, and 50 mg/kg/dose BID) by oral gavage showed limited to slight-to-moderate material in the cage pan at ≥30 mg/kg/day, indicative of vomiting. LQT-1213 related cardiovascular effects were observed and included dose-dependent and transient decreases in blood pressure (by 12 and 20 mm Hg, at the 5 mg/kg BID and 50 mg/kg BID doses; the maximal reductions [maximum change relative to baseline adjusted controls] were 17 and 27 mm Hg,

respectively) and presumed compensatory increases in HR beginning at 0.5 hours postdose and continuing until 5 hours postdose. No other meaningful cardiovascular effects or changes in temperature were observed. However, clinically meaningful blood pressure reductions have not been observed to date in the first-in-human single dose study (completed) and the multiple-ascending dose study (completed). No other meaningful cardiovascular effects or changes in temperature were observed.

3.4. Dose Rationale

3.4.1. Part 1

The 3 times a day (TID) dosing regimen and dose selection is based on PK modeling using data from the ongoing single-ascending dose/multiple-ascending dose study LQT-1213-0059 to achieve similar concentration at the end of the dosing interval (C_{trough}) levels in the general range of 250 to 620 ng/mL while slightly reducing the maximum observed plasma concentration (C_{max}). These levels were chosen to provide multiples of the whole cell SGK-1 IC₅₀ for inhibition of 89 ng/mL. The model is based on the single-and multiple-dose study with BID dosing in healthy subjects. The high dose of LQT-1213 used in this study will be equal to or lower than the maximum dose that has been evaluated in the multiple-ascending dose study (daily dose of 2.24 mg/kg/day). The LQT-1213-0059 study is ongoing at the time of finalization of this protocol, so the actual low, mid, and high doses of LQT-1213 to be used in this study will be determined before dosing with LQT-1213 but will not exceed 2.24 mg/kg/day.

3.4.2. Part 2

The TID dosing regimen and dose selection is based on the PK data obtained from the ongoing single-ascending dose/multiple-ascending dose study LQT-1213-0059. LQT-1213 dose used in Part 2 will be equal to or lower than the maximum dose that has been evaluated in the multiple-ascending dose study (daily dose of 2.24 mg/kg/day). The actual dose of LQT-1213 to be used in Part 2 will be determined before dosing with LQT-1213 but will not exceed 2.24 mg/kg/day.

3.5. Dofetilide

Dofetilide is a potent, pure inward-rectifier potassium channels (I_{Kr}) blocker with current indications for the conversion of atrial fibrillation/flutter, and for maintenance of normal sinus rhythm in patients with atrial fibrillation/flutter of greater than 1 week duration who have been converted to normal sinus rhythm. The PK, pharmacodynamic (PD), and safety profile of the commercially available formulation of dofetilide has been well characterized in prior studies, making it a good candidate for characterization of the

interplay between Ikr and late sodium current in cardiac repolarization.

The dose selection for dofetilide reflects the maximum dose approved in the United States (US) product label. The safety of this dose, in addition to its PK, PD, and safety profile, has been demonstrated in several cohorts of healthy subjects (Allen et al 2000; Johannesen et al 2014; Le Coz et al 1995; Tham et al 1993). Dofetilide was shown to be well absorbed with a systemic bioavailability >90%, to reach mean C_{max} in 2.6 hours, and to have a terminal elimination half-life of about 8 hours (Allen et al 2000; Tham et al 1993).

3.6. Study Rationale

This is a Phase 1b/2a, 2-part study.

3.6.1. Part 1

This is a Phase 1b, randomized, double-blind, crossover, dose-escalation, placebo-controlled study to evaluate the safety, tolerability, PK, and PD of SGK-1 kinase inhibition by LQT-1213 on dofetilide-induced QTc prolongation in healthy adult subjects. To avoid any issues with carryover, a washout period of at least 4 days between doses or at least 5 times the half-life of LQT-1213 will be utilized.

3.6.2. Part 2

This will be a Phase 2a, single-blind, multiple-dose safety study to evaluate the safety, tolerability, and PK of LQT-1213 in participants diagnosed with LQT2 or LQT3. The ability to attenuate QT prolongation in LQT2 and LQT3 is the basis for the anticipated effect of LQT-1213 in this proposed study. All participants with LQT2 or LQT3 will have a QTc by Fridericia's formula (QTcF) ≥480 and ≤560 ms. Up to 12 participants with LQT2 and up to 12 participants with LQT3 will be enrolled, of which the first 2 participants for each LQT subtype require having an ICD, which must have had ICD implantation at least 2 months before Screening. After initial screening which may be conducted remotely by the clinical research unit (CRU), individual participants with LQT2 or LQT3 will undergo a 1-day, single-blind placebo run-in period followed by LQT-1213 administered TID.

This study has been designed to minimize potential risk to participants. The short dosing duration was chosen to reduce any potential long term exposure risk to participants while maintaining the ability to assess the objectives of this study. Given the inpatient setting of this study, participants will be closely monitored clinically, electrographically, and by laboratory assessments during the treatment period. Furthermore, safety data obtained in Part 1 of this protocol did not suggest any safety signals or trend and is considered

supportive of this current design.

4. Study Objectives

4.1. Part 1

Part 1 is a randomized, double-blind, crossover, dose-escalation, placebo-controlled study in 28 healthy adult subjects with the following objectives:

- Primary: To evaluate the effect of oral LQT-1213 on dofetilide-induced QTc prolongation in healthy adult subjects
- Secondary: To evaluate the safety and tolerability of a combination of oral dofetilide and oral LQT-1213 in healthy adults
- Secondary: To determine the PK of oral LQT-1213 and oral dofetilide in healthy adults

4.2. Part 2

Part 2 is a single-blind, multiple-dose study in up to 12 adult participants with LQT2 and in up to 12 participants with LQT3 with the following objectives:

- Primary: To evaluate the safety and tolerability of oral LQT-1213 in participants with LQT2 or LQT3
- Secondary: To determine the PK of oral LQT-1213 in participants with LQT2 or LQT3
- Exploratory: To evaluate the correlation between the PK of LQT-1213 and candidate SGK-1 protein targets in participant peripheral blood mononuclear cells (PBMCs) in order to derive PK/PD relationships between drug exposure and target engagement; additional exploratory PD endpoints may be assessed

5. Investigational Plan

5.1. Study Design

This is a Phase 1b/2a, 2-part study; Part 1: randomized, double-blind, crossover, dose-escalation, placebo-controlled study to evaluate the safety, tolerability, PK, and PD of SGK-1 kinase inhibition by LQT-1213 on dofetilide-induced QTc prolongation in healthy adult subjects. Part 2: single-blind, multiple-dose safety study to evaluate the safety, tolerability, and PK of LQT-1213 in patients diagnosed with LQT2 or LQT3.

5.1.1. Part 1

This is a 2-treatment, 2-period crossover study. Approximately 28 healthy subjects, with the attempt to balance for sexes, will be enrolled to complete approximately up to 20 subjects in the study. Additional subjects may be enrolled to compensate for subjects that do not complete both treatment periods, at the discretion of the sponsor. The exact number will be determined during the conduct of the study. A sentinel group of up to 5 subjects may be enrolled first if warranted by the principal investigator.

In both treatment periods, all subjects will receive dofetilide on Days 1 and 2 of each period. Randomization will take place before Day 3 of Period 1. Subjects will be randomly assigned to 1 of 2 treatment sequences (AB or BA), with treatment arms as follows:

- Arm A: Dofetilide 500 μ g BID (2 × 250 μ g capsules), orally (Days 1-8) and LQT-1213 3 times a day (TID). LQT-1213 or matching placebo dosing:
 - Low dose: 3 doses on Day 3 and the first 2 doses on Day 4
 - o Mid dose: Last dose on Day 4, 3 doses on Day 5, and the first 2 doses on Day 6
 - High dose (not to exceed 0.747 mg/kg TID, daily dose 2.24 mg/kg/day): Last dose on Day 6, 3 doses on Day 7, and the first dose on Day 8. The specific doses will be determined before administration of the first dose of LQT-1213.
- Arm B: Dofetilide 500 μg BID (2 × 250 μg capsules), orally (Days 1-8) and placebo matched to LQT-1213 TID (Days 3-8)

Note: Only 1 dose of dofetilide and LQT-1213 (or placebo) will be administered on Day 8.

Screening will occur within 28 days of CRU admission. In both treatment periods, subjects will be domiciled starting 2 days before dofetilide dosing until after the last doses of dofetilide and LQT-1213 or placebo matched to LQT-1213 (Days –2 through 8). Days 1 and 2 are to establish near-steady state dofetilide plasma

levels and observe the OTc response to dofetilide. On Day 1 at 3 hours postdose in Period 1 only, the OTcF will be measured in the 3 (triplicate) ECGs and the mean value calculated. Measurements will be manually confirmed by a cardiologist who is specifically trained and experienced in ECG interval measurements. The ECG measurements at baseline and at the 3-hour time points will be performed by the same technician and cardiologist. If the mean QTcF increase is <25 ms on the triplicate safety ECGs compared with the mean from baseline (triplicate -30 min and triplicate -15 min), the subject will be discontinued from the study. If on Day 1 at 3 hours postdose in Period 1 only, the mean OTcF on the triplicate ECGs, when repeated within 30 minutes and manually confirmed by a cardiologist specifically trained and experienced in ECG interval measurements, has a mean value on the 3 (triplicate) repeated ECGs > 80 ms from the mean baseline QTcF, the dose of dofetilide will be reduced to 250 µg BID. If the mean QTcF is >500 ms on Day 1 in Period 1 only (repeated in triplicate within 30 minutes with a QTcF \geq 500 ms), the dose of dofetilide will be reduced to 250 μ g BID. If the safety ECGs (repeated in triplicate within 30 minutes) shows a mean value on the 3 (triplicate) repeated ECGs of a QTcF of >500 ms on Day 2 or afterwards (or any time in Period 2), the subject will be discontinued from the study. All ECGs for these safety assessments must be manually confirmed by a cardiologist who is specifically trained and experienced in ECG interval measurements before actions are taken. If the dose is reduced to 250 ug BID, this will be the dose used in Period 2. Note: If the subject has a new QRS >110 ms or a new bundle branch block, then an adjusted QTcF will be utilized to account for the widened QRS interval (Adjusted QTcF = QTcF [ms] – [QRS interval [ms] - 90 [ms]).

LQT-1213 or placebo matched to LQT-1213 will be administered at time 0, immediately after the 7.75-hour ECG extraction time point, and at 17 hours, though these time points may be adjusted based upon emerging data. Subjects will be discharged from the CRU on Day 9 or 10 (safety washout) in each period, if the QTcF is <460 ms and the increase from baseline is <40 ms. Day 10 evaluations will be performed if the subject is not discharged on Day 9. There will be a washout of at least 4 days (or at least 5 times the half-life) after the last dose of study drug. Subjects will return to the CRU on Day –2 and crossover to receive the alternate treatment in Period 2.

Approximately 7 days after the end of treatment in Period 2, the Follow-up Visit will be conducted remotely via telephone call.

Full PK sampling for dofetilide and LQT-1213 will be conducted on Days 4, 6, and 8 of each period. Continuous 12-lead 24-hour Holter data will be collected at the approximate 90-minute time point on Day –1 (corresponding to predose on Day 1) and stored, and on Day 1 starting 2 hours before dosing through Day 8. On each day, the Holter data card will be removed and a new one inserted 90 minutes before dosing. The ECGs will be extracted from the Holters on specific days and time points for core laboratory analysis, as detailed in the Part 1 PK and PD time points table (Section 8.3, Appendix C).

LOT-1213

Confidential

Subjects will have an overnight fast on Days –1 through Day 8 and will remain fasted until immediately after the 6-hour ECG extraction, when a light meal will immediately be provided, followed by a meal immediately after the 9.5- and 12-hour ECG extraction time points.

[figure not shown]
Subjects will fast after the meals at 6 and 9.5 hours are completed, which must be within 20 minutes for these 2 time points. Subjects can eat at will after the 12-hour meal, a light meal will be provided, which must be completed to ensure the overnight fasting requirement is met (6-hour fast), (no food or fluid except water). Serum potassium and magnesium will be checked each day on Days –1, 1, and 2 and thereafter, beginning on Day 3, potassium and magnesium will be checked every other day. Potassium <3.8 mg/dL and magnesium <1.9 mg/dL will result in additional electrolyte supplementation. It is preferred, especially on Days 1, 4, 6, and 8, that this be done in the evening (after the 12-hour time point). Electrolyte supplementation is allowed at any time as long as it is >4 hours before dosing.

Safety assessments will include AEs, clinical laboratory test results, vital signs measurements, and safety 12-lead ECG findings. Bedside safety 12-lead ECGs will be collected by the CRU staff and reviewed by the investigator; 12-lead ECGs will be classified as normal or abnormal not clinically significant or abnormal clinically significant. The safety ECG data, including all time points, will be recorded on the electronic case report form, and be used for evaluating general safety of the subjects during study and for evaluation of an AE. The ECGs extracted from Holters and analyzed by are the primary ECG data for the analysis of the ECG intervals of the study, once completed.

The dosing, meal timing, and PK and ECG time points and extractions may be modified based on emerging data.

Stopping rules will be predefined and evaluated after each successive dosing group.

Figure 5-1 Study Schematic - Part 1

Abbreviations: BID, twice daily; CRU, clinical research unit; ECG, electrocardiogram; EOS, end of study; ET, early termination; F/U, follow-up; QTcF, QT interval corrected for heart rate by Fridericia's formula; TID, 3 times a day.

- a Randomization will take place before Day 3 of Period 1.
- b On Day 1 at 3 h in Period 1 only, the QTcF will be measured in the 3 ECGs and the mean value calculated. Measurements will be manually confirmed by a cardiologist who is specifically trained and experienced in ECG interval measurements. The ECG measurements at baseline and at the 3-h time points will be performed by the same technician and cardiologist. If the mean QTcF increase is <25 ms on the triplicate safety ECGs compared with the mean from baseline (triplicate -30 min and triplicate -15 min), the subject will be discontinued from the study. If on Day 1 in Period 1 only at 3 h postdose, the mean QTcF on the triplicate ECGs, when repeated within 30 min and manually confirmed by a cardiologist specifically trained and experienced in ECG interval measurements, is >80 ms from the mean baseline QTcF, the dose will be reduced to 250 μg BID. If the mean QTcF is >500 ms on Day 1 (repeated in triplicate within 30 min), the dose will be reduced to 250 μg BID.
- c If the safety ECGs (repeated in triplicate within 30 min) shows a mean QTcF of >500 ms on Day 2 or afterwards, the subject will be discontinued from the study. Subjects can be discharged from the CRU once the QTcF is <500 ms or the increase from baseline is <40 ms. All ECGs for these safety assessments must be manually confirmed by a cardiologist who is specifically trained and experienced in ECG interval measurements before actions are taken. If the dose is reduced to 250 µg BID, this will be the dose used during Period 2 of the study. Note: If the subject has a new QRS >110 ms or a new bundle branch block, then an adjusted QTcF will be utilized to account for the widened QRS interval (Adjusted QTcF = QTcF [ms] [QRS interval [ms] 90 ms]).
- d Only 1 dose of dofetilide, LQT-1213, and placebo matched to LQT-1213 will be administered on Day 8.
- e Subjects will be discharged from the CRU on Day 9 or 10 (safety washout) in each period if the QTcF is <460 ms and the increase from baseline is <40 ms. Day 10 evaluations will be performed if the subject is not discharged on Day 9.

- f There will be a washout of at least 4 days (or at least 5 times the half-life) after the last dose of study drug. Subjects will return to the CRU on Day -2 and crossover to receive the alternate treatment in Period 2.
- g Approximately 7 days after the end of treatment in Period 2, the Follow-up Visit will be conducted remotely via telephone call.

5.1.2. Part 2

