Pharmacokinetics: The analysis will be detailed in the SAP which will be finalized before database lock. Data will be listed and summarized, where applicable. Plasma concentrations of LQT-1213 will be listed and summarized by LQT subtype for each sample time point using descriptive statistics. Mean and individual LQT-1213 concentration-time profiles will be presented in figures on linear and semilogarithmic scales. Pharmacokinetics/Pharmacodynamics: Details of the potential PD (SGK-1 protein targets) analyses to derive PK (LQT-1213)/PD relationships between drug exposure and target engagement will be provided in a separate analysis plan.

Sample size:	Part 1: Based on the calculation of the sample size for a Thorough QT study (Zhang and Machado, 2008), as the test is performed at 5 time points separately, a 1 sided 5% significance level (with adjusted 1-sided significance levels of 5%, 2.5%, 1.67%, 1.25%, and 1%) is used along with a within-subject SD of 8 ms for ΔQTcF for all treatment groups. A sample size of 20 evaluable subjects in a crossover design who complete the study will provide a power of 90% to detect 7 ms QTc effect, ie, the lower bound of all the 2 sided 90% CIs on ΔΔQTcF will exceed 7 ms at least 1 of the 5 prespecified time points. Multiplicity will be controlled by using a Hochberg procedure (Hochberg 1988). Twenty-eight subjects will be enrolled to account for dropouts.
	Part 2: In this exploratory safety study, up to 12 participants with LQT2 and up to 12 participants with LQT3 will be recruited. The sample size was not estimated based on statistical considerations but was considered sufficient to achieve the primary safety objectives of the study.
Date of protocol:	05 December 2023

2. List of Abbreviations

Abbreviation	Definition
ΔΔΗR	time-matched, placebo-adjusted, change from baseline in HR
$\Delta\Delta QRS$	time-matched, placebo-adjusted, change from baseline in QRS
ΔΔQΤc	time-matched, placebo-adjusted, change from baseline in QTc
$\Delta\Delta QTcF$	time-matched, placebo-adjusted, change from baseline in QTcF
$\Delta\Delta PR$	time-matched, placebo-adjusted, change from baseline in PR
Δ HR	change from baseline in heart rate
ΔQRS	change from baseline in QRS
ΔQTc	change from baseline in QTc
$\Delta QTcF$	change from baseline in QTcF
$\Delta QTcI$	change from baseline in QTcI
$\Delta QTcP$	change from baseline in QTcP
ΔPR	change from baseline in PR interval
λ_{z}	apparent terminal rate constant

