5.3. Withdrawal of Subjects from the Study

5.3.1. Reasons for Withdrawal

Parts 1 and 2: The primary reason for treatment discontinuation will be noted using the following categories:

- 1. Adverse event: The subject experiences an AE that, in the opinion of the investigator, requires early termination. If a subject is discontinued from the study due to an AE, the investigator or designee will be required to follow-up with the subject until the event resolves or becomes stable. If a subject dies during the study, the cause of death will be reported as a serious AE (SAE), with an outcome of death noted on the eCRF.
 - Additionally, refer to Section 5.4.3.5 for safety 12-lead ECG discontinuation criteria.
- 2. Stopping criterion: The subject meets one of the stopping criteria for individual subjects (Section 5.3.3).
- 3. Protocol deviation/violation: The subject fails to meet protocol entry criteria or does not adhere to protocol requirements, and continued participation poses an unnecessary risk to the subject's health.

Note: For **Part 1** only, if the safety ECGs (repeated in triplicate within 30 minutes)

Version 7.0

shows a mean QTcF of >500 ms on the repeated (triplicate) ECGs on Day 2 or afterwards, which will be manually confirmed by a cardiologist who is specifically trained and experienced in ECG interval measurements, the subject will be discontinued from the study. Details for subject discontinuation from the study and QTcF adjustment for a new QRS >110 ms or a new bundle branch block are provided in Section 5.3.3.

4. Voluntary withdrawal of consent: The subject wishes to withdraw from the study for any reason.

Note: Withdrawal due to an AE will not be recorded in the voluntary withdrawal category.

- 5. Study termination: The sponsor, institutional review board (IRB), Food and Drug Administration (FDA), or other regulatory agency terminates the study.
- 6. Pregnancy: The subject is found to be pregnant.

Note: If the subject is found to be pregnant, the subject is to be withdrawn immediately. The pregnancy will be followed to term, and the outcome, including premature termination, will be recorded. A second follow-up will be performed after 30 calendar days of pregnancy outcome.

7. Other.

Note: This category includes withdrawals caused by an accidental or a medical emergency, unblinding, or other rare cases. The specific reasons will be recorded on the eCRF.

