5.3.2. Handling of Withdrawals

Parts 1 and 2: The investigator may terminate a subject's study participation at any time during the study if the subject meets any of the withdrawal criteria described in Section 5.3.1. Should a subject's participation be discontinued, the primary reason for termination must be recorded. In addition, efforts will be made to perform all early termination procedures specified in the schedule of events (Section 8.1, Appendix A and Section 8.2, Appendix B). The AE eCRF will be completed for each AE.

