5.3.3. Stopping Criteria for Individual Subjects

5.3.3.1. Part 1

A subject will be withdrawn from the study if he or she meets any of the following criteria:

• Alanine aminotransferase ≥5 × ULN, confirmed on a repeat measurement, 05 December 2023 Page 60 of 117 not due to an obvious nondrug etiology.

• ECG criteria

Note: The QTcF is always used, regardless of the HR.

IMPORTANT: When evaluating the safety signals below, the QTcF or arrhythmia must be confirmed by a cardiologist who is specifically trained and experienced in ECG interval measurements or a cardiac electrophysiologist.

- o Torsades de Pointes associated with a QTcF >500 ms
- Repetitive pause-dependent ventricular ectopy associated with at least a 35% increase in the QTc interval.
- O Potential dose-down titration. Note: These measurements will be manually confirmed by a cardiologist specifically trained and experienced in ECG interval measurements. The ECG measurements at baseline and at 3 hours postdose on Day 1 of Period 1 will only be evaluated by the same technician and cardiologist. If on Day 1 at 3 hours postdose in Period 1 only, the mean QTcF on the triplicate ECGs, when repeated within 30 minutes, show a mean increase >80 ms from the mean baseline QTcF on the 3 (triplicate) repeated ECGs, the dose of dofetilide will be reduced to 250 µg BID.
- o If at any time after the first dose of dofetilide, a subject develops a QTcF >500 ms, 2 additional ECGs will be immediately performed, and then the ECG will be repeated approximately 30 minutes later, in triplicate. Note: If the subject has a new QRS >110 ms or a new bundle branch block, then an adjusted QTcF will be utilized to account for the widened QRS interval (Adjusted QTcF = QTcF [ms] − [QRS interval [ms] − 90 ms]). If the mean QTcF increase of the triplicate ECGs is confirmed (mean QTcF of the 3 (triplicate) repeated ECGs is >500 ms):
 - If this occurs on Day 1, the dose of dofetilide will be reduced to 250 μg BID.
 - If this occurs on Day 2 or afterwards (or any time in Period 2), the subject will be discontinued from the study.

Findings that meet any of these criteria should be reported to the sponsor immediately.

5.3.3.2. Part 2

A participant with LQT2 or LQT3 will be withdrawn from the study if he or she meets any of the following criteria:

- Alanine aminotransferase (ALT) or aspartate transaminase (AST) ≥8 × upper limit of normal, confirmed on a repeat measurement, not due to an obvious nondrug etiology.

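### In Part 1, Figure 5-1 footnote c appears to let a subject discontinued for QTcF above 500 ms leave the unit at 499 ms, while scheduled discharge requires QTcF below 460 ms and a rise below 40 ms

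*Protocol*

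**What the plan says.** Two discharge rules for Part 1 stand in the current Protocol text.

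- **Figure 5-1, footnote c.** It opens with the discontinuation rule: a repeated triplicate ECG that "shows a mean QTcF of >500 ms on Day 2 or afterwards, the subject will be discontinued from the study". The next sentence is the release rule: "Subjects can be discharged from the CRU once the QTcF is <500 ms or the increase from baseline is <40 ms". It names no day and no subgroup.
- **Figure 5-1, footnote e.** "Subjects will be discharged from the CRU on Day 9 or 10 (safety washout) in each period if the QTcF is <460 ms", with a rise from baseline below 40 ms as a second required condition. Section 5.1.1 and the synopsis give the same pair of conditions for Day 9 or 10: "if the QTcF is <460 ms and the increase from baseline is <40 ms".

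Section 5.3.3.1 repeats the discontinuation rule for a confirmed mean above 500 ms ("If this occurs on Day 2 or afterwards (or any time in Period 2), the subject will be discontinued from the study") but gives no discharge limit. Section 5.3.2 says that, for anyone who stops early, "efforts will be made to perform all early termination procedures specified in the schedule of events". That schedule is not in the text available for this review, and neither is the schematic that carries the footnote markers.

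**The concern.** The two rules differ in the threshold (500 against 460 ms) and in the connective (*or* against *and*). If footnote c covers subjects discontinued for QTcF above 500 ms, the people with the most prolongation after dofetilide face a lower bar for release than those who finished without trouble. The bar is also the value that triggered their removal, so a fall of a few milliseconds satisfies it. The Protocol itself treats 500 ms as a danger line: Sections 5.3.3.1 and 5.3.4.1 use QTcF above 500 ms in the Torsades de Pointes criteria. At stake is a safety release limit for healthy volunteers, not an estimate or a test.

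**Working it through.** The Protocol gives no figure to reproduce here. The check compares the two rules over a plausible range of baselines.

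**Inputs**
- Footnote c: release if QTcF < 500 or QTcF − B < 40, where B is the subject's baseline.
- Footnote e, Section 5.1.1 and the synopsis: release on Day 9 or 10 if QTcF < 460 and QTcF − B < 40.
- Discontinuation trigger: confirmed mean QTcF > 500 ms (footnote c, Section 5.3.3.1).
- Baseline range, an assumption: 400 to 440 ms. This comes from Part 1 exclusion criterion 8, taking its *and* between the two QTcF limits as *or*. The criterion applies at Screening and Day −2, so a Day 1 predose baseline could lie somewhat outside the range.

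**Step 1: reduce each rule to one limit**
- Footnote c: QTcF < max(500, B + 40). For B from 400 to 440, B + 40 is 440 to 480, so the maximum is always 500. The 40 ms condition has no effect unless B exceeds 460.
- Day 9/10 rule: QTcF < min(460, B + 40).

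**Step 2: a subject discontinued at 501 ms (whole milliseconds)**

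| B | Highest QTcF at release, footnote c | Rise over B at 499 | Highest QTcF meeting the Day 9/10 limits | Fall needed, footnote c | Fall needed, Day 9/10 limits |
|---|---|---|---|---|---|
| 400 | 499 | 99 | 439 | 2 | 62 |
| 410 | 499 | 89 | 449 | 2 | 52 |
| 420 | 499 | 79 | 459 | 2 | 42 |
| 430 | 499 | 69 | 459 | 2 | 42 |
| 440 | 499 | 59 | 459 | 2 | 42 |

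**Step 3 (secondary): footnote c read as covering everyone**

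The limits then differ by 499 − 439 = 60 ms at B = 400, 499 − 449 = 50 ms at 410, and 499 − 459 = 40 ms at 420 to 440. Those would be direct contradictions of footnote e, Section 5.1.1 and the synopsis.

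**Step 4: extra time in the unit under the stricter limit**

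Assume the rise over baseline halves every T hours once dofetilide stops. The extra hold beyond footnote c is T × log2[(499 − B)/(q − B)], where q is the highest QTcF meeting the Day 9/10 limits. It does not depend on the peak QTcF.

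- T = 8 h (the dofetilide half-life in Section 3.5): B = 400, 8 × log2(99/39) = 10.8 h; 410, 9.5 h; 420, 8.1 h; 430, 10.0 h; 440, 8 × log2(59/19) = 13.1 h.
- T = 16 h (slower recovery): 21.5, 19.0, 16.3, 20.0 and 26.2 h.

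Nights are counted from Day −2, with no Day 0. A subject discontinued on Day 2 and held to Day 4 stays 5 nights; one discontinued on Day 8 and held to Day 10 stays 11. Section 5.5.8.1 already plans for up to 11.

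**The case against.** The strongest reply is that footnotes c and e are two rules for two situations. Footnote c is the discontinuation footnote, and footnote e covers scheduled discharge; if c applied to everyone, e would have no function. The wording of c is also permissive, so nobody is obliged to release a subject at 499 ms. The footnote requires a cardiologist to confirm the safety ECGs before action, early termination procedures are to be attempted, and a subject stopped for an adverse event is to have "follow-up with the subject until the event resolves or becomes stable". The footnote markers and the schedule of events, which could settle the scope, are not available here. Part 1 also looks finished: Section 3.6.2 speaks of safety data already obtained from it.

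Most of this stands. A reader might infer that the Protocol flatly contradicts itself on discharge. The documents do not establish that, because the narrow scope is the more natural one and the two rules can then coexist.

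A reader might also infer that measurement noise would often release someone still truly above 500 ms. The documents do not support a probability for that. They give no repeatability figure for bedside triplicate ECGs, and QTcF should be falling once dofetilide has stopped.

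The reply does not rescue the limit itself. The narrow reading is the one that puts release at the trigger. Cardiologist confirmation checks the measurement, not the threshold. The follow-up duty in Section 5.3.1 sits under the adverse-event reason; meeting a stopping criterion is a separate reason there, so the duty is not expressly attached to it.

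**Conclusion.** The point holds as a poorly set safety limit of uncertain scope. On the most natural reading, a subject discontinued at 501 ms may be released after a 2 ms fall, 59 to 99 ms above baseline. The Protocol's own scheduled-discharge limits would require a fall of 42 to 62 ms. These are distances between limits, not a count of people affected; nothing in the documents shows that anyone was released at such a value. The figures rest on a baseline of 400 to 440 ms, and the 40 ms condition stays without effect for any baseline up to 460 ms. An early-discharge rule in the unavailable schedule of events could change the conclusion. Practical reach is limited because Part 1 dosing appears complete. No endpoint, power or error rate depends on it.

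**What to change.** In footnote c, limit the discharge sentence to subjects discontinued early for a confirmed mean QTcF above 500 ms, and require both QTcF below 460 ms and a rise from baseline below 40 ms before they leave. Repeat that limit in Section 5.3.3.1, which has none. Because rewording protects nobody if dosing is over, also state in the Part 1 clinical study report which discharge limit was applied to these subjects.

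The cost is a sentence or two in the Protocol and one in the report. Had the stricter limit applied, a few subjects might have stayed longer: about 8 to 13 hours if the prolongation halves every 8 hours, or about 16 to 26 hours if it halves every 16. A two-day hold after discontinuation fits within the confinement already planned.
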